#### 9.4.4 ANALYSIS OF THE SECONDARY AND TERTIARY ENDPOINTS

Secondary endpoints will be compared between the study drug and placebo groups using the per-protocol population. Serum and CSF EET/DHET ratios and biomarkers will be presented as

the mean and standard deviation, and differences evaluated with two sample Student's t-test with a two-sided type 1 error rate of 0.05%.

Tertiary endpoints will be compared descriptively between the groups based on the mean, median, standard deviation and range.

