**Justification:** EETs are degraded to inactive byproducts DHETs by the enzyme sEH. sEH activity has previously been measured after exposure to the study drug, and found to reach steady state level of >95% drug inhibition at 7 days. Prior evaluations of drug efficacy have used indirect means to measure drug effectiveness in inhibiting exogenous EETs degradation. We will directly measure *in vivo* EETs levels after drug administration to determine the degree by which sEH inhibition results in measurable increases in systemic EETs. Endogenous EETs have a very short half-life and require rapid sample processing and meticulous storage conditions.

We have chosen to measure the EET/DHET ratio due to the normal fluctuations of EETs levels in the post-bleed period after SAH. The drug will be deemed effective if we measure higher EET/DHET ratio in the treatment group compared to placebo, i.e. higher EETs suggests decreased metabolism by sEH. It is possible that serum EET/DHET ratio will not be measurably increased. EETs have a very short serum half-life (minutes), and the most plausible site of action is at the neurovascular unit.

To more precisely estimate sEH enzyme activity in plasma, we will also measure the metabolism of more stable lipid substrates of sEH: EPOME, and the metabolic byproduct DPOME. Serum EPOME and DPOME levels have previously been used to measure the hydrolase activity of sEH.[13]

We will also determine whether there are CNS effects of the drug, either via direct measurement of increased EET/DHET ratio in the CSF, or via downstream effects on the inflammatory profile in the CSF and on the markers of endothelial dysfunction. This is particularly important because in healthy subjects and animals, the drug does not cross the blood brain barrier. It is possible that EETs have a localized action on the endothelium and vascular smooth muscle, without crossing the blood brain barrier. sEH inhibition may exert anti-inflammatory and vasodilatory effects at this site without changing measurable CSF EETs levels. If this is the case, we expect to detect differences in CSF inflammatory markers.

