We anticipate a possible effect of the study drug in CSF for the following reasons: 1) There is breakdown of the blood brain barrier following SAH and both lipid and non-lipid soluble molecules may be able cross the neurovascular unit due to increased permeability; and 2) Endothelial-derived cytokines and mediators may be transported across compartments, including blood, perivascular space, and CSF. It will be important to confirm the site of action of the study drug is only at the endothelium level or if its effects on the central nervous system

We will collect biomarkers at multiple time points because eicosanoid levels, endothelial dysfunction, and the inflammatory response vary significantly over the natural course of subarachnoid hemorrhage. We may control for significant variations at baseline when interpreting the results.

- **Tertiary Objective:** Provide preliminary estimates of clinically relevant endpoints to inform the design of a larger trial.

We will collect clinical measurements on outcomes throughout the treatment course, at hospital discharge and at 90-day follow-up. To assess DCI directly, we will measure daily middle cerebral artery (MCA) transcranial Doppler flow velocities and the degree of angiographic vasospasm. We will also measure acute changes in neurologic exam, the need for therapeutic interventions for DCI, and new stroke on imaging at discharge. We will also measure more objective surrogate outcomes at hospital discharge and 90-day follow-up including: hospital length of stay, discharge disposition, modified Rankin Scale (mRS), and the extended Glasgow Outcome Scale (GOSE).

**Justification:** This study is not powered to detect an effect of drug administration on these endpoints, but these data will provide information for sample size calculations in larger subsequent studies.

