## 8.5 PHARMACODYNAMIC EFFECT ASSESSMENTS

### 8.5.1 SAMPLE COLLECTION

Blood samples will be collected from study participants after randomization but prior to administration of the first dose of study drug or placebo, and again on study day 7 and study day 10. For patients with an external ventricular drain (EVD), cerebrospinal fluid (CSF) will be collected at each timepoint as well.

10 mL of blood and 5 mL of CSF will be collected at each time point. If the indwelling external ventricular drain is removed prior to study day 10, CSF samples will be collected on the day of planned removal. In the event of inability to collect CSF due to obstructed catheter, or low intracranial CSF volume, one additional attempt will be allowed within a period of 24 hours.

Blood samples will be collected by the bedside nurse and processed for storage by study personnel. CSF samples will be collected by physician medical staff, from external ventricular drainage access, and then processed for storage by study personnel.

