#### Secondary Endpoints: Blood and CSF biomarkers of drug pharmacodynamic effect

- Day 7 serum EET/DHET ratio
- Day 7 CSF EET/DHET ratio
- Day 7 CSF inflammatory cytokines
- Day 7 serum endothelial injury biomarkers
- Day 7 serum EPOME/DPOME ratio
- Day 10 serum EET/DHET ratio
- Day 10 CSF EET/DHET ratio
- Day 10 CSF inflammatory cytokines
- Day 10 serum endothelial injury biomarkers
- Day 10 serum EPOME/DPOME ratio

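### The pharmacodynamic comparison reads as an unadjusted raw-scale t-test that leaves the pre-dose sample unused; a pre-specified log-scale ANCOVA would be a cheap improvement

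*Combined protocol and SAP*

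**What the plan says.** Section 9.1 defines the secondary endpoints as values on a day, for example "Day 7 serum EET/DHET ratio", and not as changes from baseline. Section 9.4.4 presents the EET/DHET ratios and biomarkers by mean and SD, with "differences evaluated with two sample Student's t-test". Neither section mentions a logarithm, a covariate or the pre-dose sample.

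That sample exists. Section 8.5.1 states: "Blood samples will be collected from study participants after randomization but prior to administration of the first dose of study drug or placebo". It adds: "For patients with an external ventricular drain (EVD), cerebrospinal fluid (CSF) will be collected at each timepoint as well". The only link to the analysis is one sentence in the Section 3 justification: "We may control for significant variations at baseline when interpreting the results".

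Section 8.5.1 also creates an off-schedule CSF sample: "If the indwelling external ventricular drain is removed prior to study day 10, CSF samples will be collected on the day of planned removal". Section 9 does not say how that sample is analysed.

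**The concern.** Concentrations and ratios are positive and often right-skewed. If they are roughly log-normal, a t-test on the raw scale loses power. If the pre-dose value also predicts the later one, ignoring it loses more.

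The comparison matters although it is secondary. Section 3 gives it a decision role: "The drug will be deemed effective if we measure higher EET/DHET ratio in the treatment group compared to placebo". The same section concedes that the serum ratio may not rise measurably, so a null result is foreseeable and its reading depends on precision. At most 30 patients are randomised. Section 9.3 then limits the secondary analyses to patients who complete all ten days of dosing, and CSF comes only from those with a drain.

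The optional adjustment does not fill the gap. It names no model, and whether it is used depends on the data observed. Timing matters too, because Section 3 says that "eicosanoid levels, endothelial dysfunction, and the inflammatory response vary significantly over the natural course of subarachnoid hemorrhage". CSF taken when a drain comes out is therefore not interchangeable with CSF from the scheduled day.

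**Working it through.** **Inputs from the documents.** Up to 30 patients, nominally 15 per arm (Section 4.1); fair-coin allocation (Section 6.3); two-sample t-test, two-sided (Section 9.4.4). The error rate is printed as 0.05%; 5% is used below and the printed value is checked at the end. The plan gives no power figure to reproduce.

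**Assumptions.** Log-normal markers; a two-fold effect; log-SD s = 0.5 or 1; correlation r between log pre-dose and log later value of 0 to 0.7, equal in both arms; 12 per arm as an example of completers and 8 per arm as an example CSF set.

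**Step 1: raw against log scale.** On the log scale the standardised difference is ln 2 / s, which is 0.693 for s = 1 and 1.386 for s = 0.5. On the raw scale the coefficient of variation is CV = √(exp(s²) − 1), and for a k-fold effect the standardised difference is (k − 1) / (CV × √((1 + k²)/2)).
- s = 1: CV = 1.311, giving 1 / (1.311 × 1.581) = 0.48 against 0.69 on the log scale.
- s = 0.5: CV = 0.533, giving 1 / (0.533 × 1.581) = 1.19 against 1.39.

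**Step 2: baseline adjustment.** ANCOVA multiplies the residual SD by √(1 − r²), loses one degree of freedom and inflates the variance by about 1 + 1/(N − 4), which is 1 + 1/26 = 1.038 at N = 30. For s = 1 and 15 per arm, the noncentrality is 0.693 × √7.5 = 1.90 for the log t-test. For ANCOVA at r = 0.5 it is (0.693/0.866) × √7.5 / √1.038 = 2.15. Adjustment breaks even near r = 0.2 at 15 per arm and near r = 0.3 at 8 per arm.

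**Step 3: simulated power** (two-fold effect, 60,000 runs per cell).

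| Per arm | Log-SD | Raw t | Log t | Log ANCOVA, r = 0 / 0.3 / 0.5 / 0.7 |
|---|---|---|---|---|
| 15 | 1 | 31% | 45% | 44 / 47 / 55 / 71% |
| 12 | 1 | 24% | 37% | 35 / 38 / 45 / 60% |
| 8 | 1 | 16% | 25% | 24 / 26 / 30 / 41% |
| 15 | 0.5 | 93% | 96% | 95 / 96 / 98 / >99% |
| 12 | 0.5 | 86% | 90% | 89 / 91 / 95 / 99% |
| 8 | 0.5 | 67% | 73% | 70 / 74 / 81 / 93% |

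**Step 4: validity and downside.** With no drug effect the raw test rejects in 3.7 to 4.8% of trials at splits from 10/20 to 20/10. It is mildly conservative, not invalid. If the raw data are in fact normal (CV 0.2 to 0.3, effect 0.8 SD, 15 per arm), taking logs costs 1 to 2 points: 56% raw against 55 to 54%.

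**Step 5: two side issues, neither proposed by the plan.**
- The plan promises no confidence interval. If a pooled 95% interval for the raw mean difference were reported for a two- to three-fold effect, coverage at 15/15 would be 94 to 93% (log-SD 0.5) or 92 to 89% (log-SD 1). At 12 drug/18 placebo it would be 91 to 88% or 89 to 84%. At 18/12 it would be 96% or 94 to 92%. Under fair-coin allocation of 30, 12 to 18 on drug has probability 80%, and 10 or fewer 4.9%.
- If the better of the adjusted and unadjusted log analyses were chosen after seeing the data, type I error would be 5.8, 6.4, 7.2 and 8.4% at r = 0, 0.3, 0.5 and 0.7. A fixed baseline pretest would not inflate it (5.0 to 3.7%).

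**Step 6: the printed error rate.** At 0.05%, with 15 per arm, a two-fold effect, log-SD 1 and r = 0.5, power is about 0.5% raw, 4% log and 6% ANCOVA. The ordering is the same, but that figure matters more than the choice of test and needs its own clarification.

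**The case against.** The strongest reply is that nothing here is wrong. A t-test in a randomised trial is valid, the endpoint is secondary, and Section 9.2 says the sample was chosen to describe safety. A geometric mean ratio also estimates something different from a difference in means. All of this stands, which is why the point is an improvement and not a correction.

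The baseline half is the less certain half. The table assumes the same correlation in both arms. With near-complete enzyme inhibition, the ratio on drug may stop tracking its pre-dose value. If r is 0.5 on placebo and 0 on drug, ANCOVA gives 46% against 45% for the log t-test at 15 per arm with log-SD 1, and 25% against 25% at 8 per arm. Section 3 also gives EETs a serum half-life of minutes. Adjustment may therefore add nothing for the ratios; this argument bears less on the downstream biomarkers.

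The plan is not blind to variability. Section 3 says the ratio was chosen because EET levels fluctuate, and Section 9.4.1 tabulates baseline characteristics, which could include pre-dose markers. Neither brings the pre-dose value into the comparison. The attached schedule and the manual of procedures are not in the text reviewed and might set a CSF window; Section 9 does not refer to one.

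**Conclusion.** The point holds as a cheap improvement. Sections 9.1 and 9.4.4 together imply an unadjusted raw-scale comparison, and the pre-dose sample has no defined part in it. At 15 per arm, a two-fold effect and a 5% level, the log scale alone adds about 14 points of power if the log-SD is 1 and about 3 if it is 0.5. Baseline adjustment then changes power by anything from a loss of 1 point (r = 0) to a gain of 26 points (r = 0.7) at log-SD 1. These figures rest on log-normality and on an assumed spread, effect and correlation, none of which the documents give. The gain may be negligible, but the downside is small and bounded. The primary safety analysis is unaffected.

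**What to change.** In Section 9.4.4, pre-specify that each ratio and biomarker, EPOME/DPOME included, is log-transformed and compared at each day by ANCOVA on treatment and the log pre-dose value of the same marker. Report an adjusted geometric mean ratio with 95% CI. State rules for:

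- a missing pre-dose value, for example the mean log pre-dose value of both arms combined, so that the patient stays in;
- values below the assay limit;
- CSF taken at drain removal, for example counted as day 7 or day 10 only within a stated window, with a sensitivity analysis that includes all such samples.

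Keep an unadjusted log-scale Welch comparison as a sensitivity analysis, and replace the optional-adjustment sentence in Section 3 with a reference to this analysis.

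The cost is a wording amendment to Sections 3 and 9.4.4, which needs IRB approval before use (Statement of Compliance), and one degree of freedom. No new samples or assays are needed. If the pre-dose value predicts nothing, ANCOVA loses about 1 to 2 points of power against the log t-test at 15 per arm and about 1 to 4 at 8 per arm. If a quarter of pre-dose values are missing at random and the pooled-mean rule is used, type I error stays at 4.9 to 5.1%. Power at 15 per arm (two-fold, log-SD 1) is then 44, 51 and 61% at r = 0, 0.5 and 0.7, against 44, 55 and 71% with complete baselines.

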### 8.5.3 INFLAMMATORY AND ENDOTHELIAL INJURY SAMPLE PROCESSING

The remaining plasma and CSF obtained at each sample collection time point will be frozen at -80°C and reserved for batch processing of the following biomarkers below. Luminex assays for the biomarkers will be processed in the OHSU Anesthesiology Core Lab at the end of the enrollment period after the last sample collection.

TABLE 1: Neuroinflammatory and endothelial injury biomarkers associated with EETs signaling

Biomarker	Role	Blood	CSF
Drug Action			
Eicosanoid Profile (EETs and DHETs)	Drug effect marker[12]	X	X
Inflammatory Biomarkers			
Tumor necrosis factor alpha (TNF-α)	Neuroinflammatory marker, apoptosis, decreased in EETs knockouts[4]		X
Interleukin 1β (IL-1β)	Neuroinflammatory marker[14]		X
Interferon gamma (IFN-γ)	Neuroinflammatory marker, decreased in sEH knockouts[4]		X
Interleukin 6 (IL-6)	Neuroinflammatory marker, associated with vasospasm,[14] decreased in sEH knockouts[4]		X
Interleukin 8 (IL-8)	Neuroinflammatory marker, associated with vasospasm[14]		X
Monocyte chemoattractant protein 1 (MCP-1)	Neuroinflammatory marker, associated with vasospasm[14]		X
Endothelial Injury			
e-selectin	Leukocyte adhesion marker[15]	X	
p-selectin	Platelet adhesion marker[16]	X	
Vascular cell adhesion marker (VCAM-1)	Vascular inflammation, blood brain barrier breakdown, hydrocephalus[17]	X	
Platelet endothelial cell adhesion marker (PECAM-1, CD31)	Leukocyte, platelet, monocyte adhesion, angiogenesis[16]	X	
Intercellular adhesion molecule (ICAM-1)	Endothelial surface marker for inflammation [16]	X	

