## 9.2 SAMPLE SIZE DETERMINATION

The total sample size was selected *a priori* based on the need to evaluate and describe the safety profile of the study drug in this patient population.

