## 9.3 POPULATIONS FOR ANALYSES

Any patient who receives a single dose of study drug will be included in safety analyses as part of the safety population. Only patients who complete 10 days of study drug administration will be included in the secondary analyses as part of the per-protocol population.

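### Section 9.4.4 sets the two-sided type 1 error for the secondary t-tests at 0.05% (alpha = 0.0005), very probably a slip for 0.05 (5%)

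*Combined protocol and SAP*

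**What the plan says.** Section 9.4.4 compares the drug and placebo groups on serum and CSF EET/DHET ratios and on the biomarkers. Means and standard deviations are reported, with "differences evaluated with two sample" Student's t-tests "with a two-sided type 1 error rate of 0.05". The figure is followed directly by a percent sign, so the stated level is 0.05%, or 0.0005.

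The tests that this governs come from two places. Section 9.1 lists ten secondary endpoint lines, beginning with "Day 7 serum EET/DHET ratio" and covering days 7 and 10. Table 1 in Section 8.5.3, titled "Neuroinflammatory and endothelial injury biomarkers associated with EETs signaling", names the individual markers: six cytokines in CSF and five endothelial markers in blood.

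The number of patients behind each test is limited in three ways:

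- Up to 30 patients are randomized equally (Section 4.1), and the total was chosen "based on the need to evaluate and describe the safety profile of the study drug in this patient population" (Section 9.2), not for power.
- "Only patients who complete 10 days of study drug administration will be included in the secondary analyses" (Section 9.3).
- CSF depends on a drain being in place: "For patients with an external ventricular drain (EVD), cerebrospinal fluid (CSF) will be collected at each timepoint as well" (Section 8.5.1).

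**The concern.** A two-sided level of 0.0005 is extraordinarily strict for small-sample pharmacodynamic comparisons in a phase 1b trial. The plan gives no reason for it: there is no multiplicity procedure, no allocation of alpha and no power calculation. No other section states a level that would correct or confirm it.

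These t-tests are the only inferential analysis in the plan; the safety and tertiary endpoints are summarised descriptively. They also bear on the proof-of-concept aim in Section 4.2. Either way of proceeding causes trouble. Followed literally, the rule can miss pharmacodynamic differences of about 1 to 1.5 SD. If the analyst assumes 5% was meant and uses it without a correction, every p-value between 0.0005 and 0.05 can be challenged as significant only against a threshold that was never prespecified.

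**Working it through.** **Inputs from the document.** Two-sample Student's t-test, two-sided, alpha written as 0.05% = 0.0005 (Section 9.4.4). Up to 30 patients, so 15 per arm if exactly balanced (Section 4.1).

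**Assumptions.** 80% power as benchmark; normal data with equal variances; differences in SD units, because the document gives no effect size or SD; 10 per arm as an illustration of a reduced analysis set. The plan states no power or detectable difference, so there is no figure of its own to reproduce.

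**Step 1. Could 0.05% be a multiplicity-adjusted level?** Count the tests. Serum EET/DHET, CSF EET/DHET and serum EPOME/DPOME make 3; six CSF cytokines and five blood endothelial markers bring the total to 14; two days give 14 × 2 = 28. EPOME/DPOME is not named in the sentence that sets the test; without it the count is 13 × 2 = 26.

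| Tests counted | Bonferroni level |
|---|---|
| 10 (endpoint lines in 9.1) | 0.05/10 = 0.5% |
| 26 | 0.05/26 = 0.19% |
| 28 | 0.05/28 = 0.18% |
| 50 (all 11 biomarkers in both fluids: (22 + 3) × 2) | 0.05/50 = 0.10% |

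Reaching 0.05% would need 0.05/0.0005 = 100 tests. None of the counts comes near that.

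**Step 2. Critical value and smallest significant observed difference.** With n per arm, df = 2n − 2, and the smallest observed standardized difference that reaches significance is t_crit × √(2/n). For n = 15, df = 28:

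- alpha 0.05: t_crit = 2.048, so 2.048 × √(2/15) = 0.75 SD
- alpha 0.0005: t_crit = 3.935, so 3.935 × √(2/15) = 1.44 SD

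**Step 3. Power.** For a true difference d in SD units, power is the probability that a noncentral t with df = 2n − 2 and noncentrality d × √(n/2) exceeds t_crit. For example, with n = 15 and d = 1.5, the noncentrality is 1.5 × √7.5 = 4.11, giving power 0.977 at alpha 0.05 and 0.574 at alpha 0.0005. The detectable difference is the d at which power is 80%.

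| | 15 per arm, 5% | 15 per arm, 0.05% | 10 per arm, 5% | 10 per arm, 0.05% |
|---|---|---|---|---|
| t_crit | 2.048 | 3.935 | 2.101 | 4.233 |
| Detectable at 80% power (SD) | 1.06 | 1.77 | 1.32 | 2.33 |
| Power at 1.0 SD | 75% | 15% | – | – |
| Power at 1.5 SD | 98% | 57% | 89% | 25% |
| Power at 2.0 SD | >99% | 92% | 99% | 60% |

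A true difference of 1.06 SD, which has 80% power at 5%, has 19% power at 0.05% with 15 per arm.

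**Step 4. Sensitivity to the numbers analysed.** At 8 per arm the detectable differences are 1.51 SD (5%) and 2.76 SD (0.05%). Section 6.3 specifies unrestricted randomization, so exact balance is not guaranteed; a 10/20 split gives 1.12 and 1.88 SD. For a total of 30, the balanced case is the most favourable.

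**Step 5. Price of 5%.** If the drug has no effect, 28 × 0.05 = 1.4 false positives are expected, and the chance of at least one is 1 − 0.95^28 = 76% if the tests are independent. For 26 tests the figures are 26 × 0.05 = 1.3 and 1 − 0.95^26 = 74%.

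**The case against.** The strongest reply is that this is a notation error with a one-line correction, and that the power loss arises only if someone really applies 0.0005, which is unlikely. The tests concern secondary endpoints in a small phase 1b trial sized for safety. Dosing, participant safety and data collection do not depend on alpha, and means and SDs are reported whatever the level. All of this is true and limits the consequences. It does not remove the defect: this figure is the decision threshold for every secondary test, and leaving it unsettled makes the reading of each result disputable.

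The justification in Section 3 says the drug will be judged effective on a higher EET/DHET ratio than placebo and mentions no significance level. Taken literally, that judgement does not depend on alpha. If it is meant to rest on the t-test, which the document does not say, the level matters more.

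The power figures assume normality and equal variances. Ratios and cytokine levels may be skewed, and tail probabilities at a critical value near 4 are sensitive to that. The figures should be read as indicating the size of the effect, not as precise forecasts. The comparison between the two levels does not turn on the second decimal.

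The test count can be argued, because the synopsis and Section 3 can be read as measuring all biomarkers in both fluids. That reading gives 50 tests and 0.10%, still twice the stated level.

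Finally, the independence behind the 76% is doubtful for repeated days and related cytokines. The expected count of 1.4 does not need independence.

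**Conclusion.** The point holds. The significance level in Section 9.4.4 is wrong as written or, if deliberate, unexplained. A slip for 0.05 is very probable, but that is an inference; only the sponsor can confirm the intended level.

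If 0.05% is applied at 15 per arm, the detectable difference is 1.77 instead of 1.06 SD, and differences of 1 to 1.5 SD, which would have 75% to 98% power at 5%, have 15% to 57%. Effects of 2 SD or more would still usually be found at 15 per arm, but not reliably at 10. Completers-only analysis and EVD-dependent CSF sampling make smaller numbers likely, above all for the CSF endpoints. These results rest on 80% power as benchmark, normal data with equal variances, and balanced arms. Because the document gives no effect size or SD for EET/DHET, the loss of power for the true effect is unknown.

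It must be fixed because it is the sole inferential threshold in the plan. It should be settled before the batch-assayed samples are unblinded and analysed.

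**What to change.** In Section 9.4.4, replace 0.05% with 0.05 (5%). If 0.05% is intended, keep it and state the rationale.

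If 5% is adopted, add that the secondary p-values are unadjusted for multiplicity. Whether to go further than that is the sponsor's choice.

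The change has no operational cost. Its statistical price is the unadjusted false-positive rate shown in step 5 of the working.

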## TERTIARY ENDPOINT ASSESSMENTS

### **Discharge and Follow-up Assessments:**

At hospital discharge and 90-day follow-up, we will also measure objective clinical surrogate endpoints. The hospital discharge assessment will be abstracted from the patient medical record and obtained from patient interview. The 90-day follow-up assessment will be obtained from phone interview with the patient or their surrogate. We will collect the following information:

- **At Hospital Discharge:**
  - **Hospital length of stay**, in days
  - **New stroke on imaging:** We will review the last head CT or other brain imaging to detect the presence of a new area of cerebral infarction. We will define a cerebral infarction identified on hospital discharge that was not present on imaging between 24–48 hours after aneurysm occlusion, and not attributable to other causes such as surgical clipping or endovascular treatment. Hypodensities resulting from extraventricular drains or residual intraparenchymal hematomas will not be considered new strokes.
  - **Discharge disposition:** We will record the disposition from the hospital in one of the following categories: home, home with services, rehab, LTAC, SNF, hospice, death
  - **Modified Rankin Scale:** We will determine and record the mRS score from where 0 – no symptoms, 1 – no significant disability, able to carry out all usual activities despite some symptoms, 2 – slight disability. Able to look after own affairs without assistance, but unable to carry out all previous activities, 3 – moderate disability, requires some help, but able to walk unassisted, 4 – moderately severe disability, unable to attend to own bodily needs without assistance, and unable to walk unassisted, 5 – severe disability, requires constant nursing care and attention, bedridden, incontinent, 6 – deceased.
- **At 90-day follow up**
  - **Modified Rankin Scale**
  - **Extended Glasgow Outcome Scale (GOSE):** At 90 day follow up, we will determine the GOSE based on a structured interview of 19 questions detailed in the variable list and assessment tools. We will record the GOSE on a scale of 1-8 where 1 – deceased, 2 – vegetative state, 3 – low severe disability, 4 – upper severe disability, 5 – low moderate disability, 6 –upper moderate disability, 7 – low good recovery, 8 – upper good recovery.

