#### Tertiary Endpoints: Clinical endpoints

- Incidence of neurologic changes attributable to DCI
- Incidence of angiographic vasospasm
- Incidence of new stroke at hospital discharge
- Hospital length of stay
- Hospital discharge Modified Rankin Scale score
- Hospital discharge disposition
- 90-day follow-up Modified Rankin Scale score
- 90-day follow-up Glasgow Outcome Scale Extended score

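### Section 9.4.4 prescribes mean, median, SD and range for all eight tertiary endpoints, but the set fits only length of stay directly and omits the distributions and intervals that planning a larger trial would need

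*Combined protocol and SAP*

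**What the plan says.** The only analysis statement for the tertiary endpoints is in Section 9.4.4: "Tertiary endpoints will be compared descriptively between the groups based on the mean, median, standard deviation and range". Section 9.1 lists eight of them:

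- **Three incidences:** "Incidence of neurologic changes attributable to DCI", "Incidence of angiographic vasospasm" and "Incidence of new stroke at hospital discharge".
- **One categorical endpoint:** discharge disposition. Under Tertiary Endpoint Assessments in Section 8 it is recorded as "home, home with services, rehab, LTAC, SNF, hospice, death", with no numeric scores.
- **Three ordinal scores:** "Hospital discharge Modified Rankin Scale score", "90-day follow-up Modified Rankin Scale score" and GOSE at 90 days. mRS runs from 0 to 6 with death as 6; GOSE runs from 1 to 8 with death as 1.
- **One numeric endpoint:** hospital length of stay, in days.

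Section 3 explains what the data are for. The study is not powered for these endpoints, but "these data will provide information for sample size calculations in larger subsequent studies". Elsewhere the plan does match format to data type: Section 9.4.3 uses number and percentage for adverse events, and mean, SD, median and range for laboratory values and vital signs.

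**The concern.** Section 9.4.4 applies the format for continuous measurements to a list in which seven of the eight endpoints are binary, categorical or ordinal. Followed literally, it gives a number with no clinical meaning for disposition. It gives a proportion without count or interval for each incidence, and summaries of mRS and GOSE from which the category distribution cannot be recovered.

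What is at stake is the tertiary objective. A later trial sized on mRS or GOSE needs either the category distribution or the rate above a cut-point. A trial sized on delayed cerebral ischemia (DCI), vasospasm or stroke needs an event rate and a sense of how uncertain it is. If only the four statistics are tabulated, whoever plans that trial must go back to the patient-level data.

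**Working it through.** The documents give no event rate, effect size or precision target for these endpoints, so there is no figure to reproduce. The sample size is up to 30 with equal randomization (Section 4.1). I assume 15 per arm; the unrestricted fair-coin procedure in Section 6.3 may give unequal arms. All event counts below are hypothetical.

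**1. Endpoint types.** 3 binary + 1 categorical + 3 ordinal = 7 of 8 for which the four statistics are not a suitable set. Length of stay is the eighth.

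**2. Disposition.** Take hypothetical counts of 4, 2, 3, 1, 3, 0, 2 in the listed order.

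- Coded 1 to 7: sum = 4 + 4 + 9 + 4 + 15 + 0 + 14 = 50 and sum of squares = 228. Mean = 50/15 = 3.33; SD = √[(228 − 50²/15)/14] = 2.09.
- Order kept, death coded 10 instead of 7: sum = 56 and sum of squares = 330. Mean = 56/15 = 3.73; SD = √[(330 − 56²/15)/14] = 2.94.

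The patients are the same; only the codes changed.

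**3. mRS.** Take two samples of 15, with counts at scores 0 to 6:

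| | A: 2, 0, 0, 7, 3, 0, 3 | B: 1, 0, 6, 1, 0, 6, 1 |
|---|---|---|
| Sum of scores | 21 + 12 + 18 = 51 | 12 + 3 + 30 + 6 = 51 |
| Sum of squares | 63 + 48 + 108 = 219 | 24 + 9 + 150 + 36 = 219 |
| Mean | 51/15 = 3.40 | 3.40 |
| SD = √[(219 − 51²/15)/14] | 1.80 | 1.80 |
| Median (8th value) | 3 | 3 |
| Range | 0–6 | 0–6 |
| mRS 0–2 | 2/15 (13%) | 7/15 (47%) |
| Deaths (mRS 6) | 3 | 1 |

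The planned table would be identical for A and B.

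**4. Incidences.** For x events in n = 15, the mean of the 0/1 variable is x/n and its SD is √[n/(n − 1) × p(1 − p)]. The exact (Clopper-Pearson) limits are the 0.025 quantile of Beta(x, n − x + 1), or 0 when x = 0, and the 0.975 quantile of Beta(x + 1, n − x).

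| Events | Mean (proportion) | SD | Exact 95% CI |
|---|---|---|---|
| 0/15 | 0.000 | 0.000 | 0 to 21.8% |
| 3/15 | 0.200 | 0.414 | 4.3% to 48.1% |
| 4/15 | 0.267 | 0.458 | 7.8% to 55.1% |
| 5/15 | 0.333 | 0.488 | 11.8% to 61.6% |
| 8/15 | 0.533 | 0.516 | 26.6% to 78.7% |

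The proportion can be read off. With N, the SD gives a standard error: for 4/15, 0.458/√15 = 0.118. The resulting normal interval, 0.267 ± 1.96 × 0.118, is 3.5% to 49.8% against the exact 7.8% to 55.1%. At 0/15 the SD is zero and the normal interval collapses, although rates up to 21.8% remain compatible with the data.

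**5. Why the interval matters for planning.** Assume a 33% relative reduction (p₂ = 0.67p₁), 80% power and two-sided 5%. With p̄ = (p₁ + p₂)/2,

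n per arm = [1.960√(2p̄(1 − p̄)) + 0.842√(p₁(1 − p₁) + p₂(1 − p₂))]² / (p₁ − p₂)².

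At p₁ = 0.333, p₂ = 0.223 and p̄ = 0.278, so n = (1.960 × 0.6336 + 0.842 × 0.6288)² / 0.1099² ≈ 260. At the two ends of the interval for 5/15, n is 919 (p₁ = 0.118) and 94 (p₁ = 0.616).

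**The case against.** The strongest reply is that this concerns table format, not lost information. Several parts of it stand:

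- The mean of a 0/1 variable is the incidence, and the endpoints are named as incidences. Section 9.4.1 also promises the size of each analysis set, so count and interval can be rebuilt when no values are missing.
- The SD of 0/1 data with N does give a standard error, so it is not empty of information, although it is crude at 15 and fails at zero events.
- Median and range are valid for mRS and GOSE. Disposition runs roughly from home to death, so calling it purely nominal is arguable and a median category could be read. The mean and SD still depend on arbitrary spacing.
- The wide intervals come from the sample size. Better summaries display that limit; they do not remove it.
- The endpoints are exploratory and compared only descriptively, and Section 3 already says the study is not powered for them.

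A reader might go further and infer that the trial will fail to produce the planning estimates it was set up to deliver. The documents do not support that. Section 4.2 describes a safety and proof-of-concept study, safety is the primary objective, and planning estimates are the tertiary one. Disposition, mRS and GOSE are recorded for each patient, so the right summaries can be produced from data already being collected.

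The reply does not rescue the sentence itself. Section 9.4.3 states number and percentage for adverse events only. DCI deteriorations and angiography results are also logged as disease-related events (Section 8.4.2), but that does not supply a tertiary summary of stroke, disposition, mRS or GOSE.

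**Conclusion.** The point holds as a mismatch between a stated rule and the endpoints it governs. The four statistics fit one endpoint of eight directly. Their mean and SD have no meaning for disposition. They are a poor format, without intervals, for three incidences, and they leave the distribution of three ordinal scores undetermined. The mRS result is exact arithmetic and needs only a sample of 15. The interval and sample-size figures rest on assumed arms of 15, hypothetical event counts and an assumed 33% relative reduction; they show scale and predict nothing.

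The consequence is limited to exploratory tertiary reporting. The primary safety and secondary pharmacodynamic analyses are untouched. The sentence should still be changed, because as written it prescribes an uninterpretable result for one endpoint and omits what the tertiary objective asks for, and the replacement costs almost nothing.

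**What to change.** Replace the sentence on tertiary endpoints in Section 9.4.4 with a rule by endpoint type:

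- **DCI-related neurologic change, angiographic vasospasm, new stroke:** n/N (%) per arm with exact 95% CI; optionally the risk difference with its CI. State N for each endpoint, since Section 2.1 describes angiography as done when indicated and not every patient may be assessable for vasospasm.
- **Discharge disposition:** count and percentage in each of the seven categories, per arm.
- **mRS (discharge and 90 days) and GOSE (90 days):** the full category distribution per arm with deaths included (mRS 6, GOSE 1), plus median and IQR. Any dichotomy can then be read off by a later planner.
- **Length of stay:** mean, SD, median and range as now planned, shown with the number of in-hospital deaths per arm, because death cuts a stay short. The median should stay.

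The cost is one paragraph of analysis text and a few extra table rows. No new data, assessments or patients are required.
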